3.2.6.2 Hospital Anxiety and Depression Scale (HADS)

HADS is a validated questionnaire containing 14 items, 7 each for anxiety and depression. Subject will rate each question ranging from 0 to 3, and the total score ranges from 0 to 21 for each sub-scale. HADS will be administered only to the subset of subjects who fluently speak a language in which the questionnaire is presented.

For each sub-scale, the score will be categorized as follows:

- 0-7 = Normal
- 8-10 = Borderline abnormal (borderline case)
- 11-21 = Abnormal (case):

HADS will be assessed at baseline, weeks 12, 24, or early termination visit when applicable.

At a given visit, there must be responses to at least 6 out of 7 questions within each sub-scale of anxiety and depression. If fewer than 6 responses, then the sub-scale will be set to missing.

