4.7.1.3 Handling of Missing Data

Use of rescue therapy: For the purpose of efficacy analysis, subjects receiving any rescue therapies will be considered as treatment failures. All efficacy data, except Observed Case (OC), will be set to missing after rescue medication is used. In OC analysis, observed data after subject has received rescue treatment will be included.

Diary data: If a subject has less than 4 diary entries in a week, the weekly prorated average scores will be set to missing.

The following methods will be used to impute the missing values:

Continuous endpoints: To impute the missing values for the primary analysis of continuous endpoints, Mixed-effect Model for Repeated Measures (MMRM) approach will be used for the primary and secondary endpoints (where applicable).

In addition, the following imputation approaches will be carried out as sensitivity analyses for primary and selected secondary endpoints to assess the robustness of findings. For sensitivity analyses, continuous endpoints will be analysed using analysis of covariance (ANCOVA) including terms of treatment group, baseline IGA severity (randomization strata), and the corresponding baseline value.

1. **Multiple imputation (MI) method under assumption missing at random (MAR):**

- a. Imputation phase: The missing data are filled in m times to generate m complete data sets. The selection of m depends on the required computing time. A reasonable range is 20 to 100 times, or may follow a rule of thumb that the number of imputations should be similar to the percentage of cases that are incomplete.
- b. Analysis phase: The m complete data sets are analyzed by using the same method as the corresponding primary analysis.

- c. Pooling phase: The results from the m complete data sets are combined for the inference.
2. **Last Observation Carried Forward (LOCF):** The last observed post-baseline value will be used to replace missing values for continuous variables. For questionnaire-based variables, LOCF will be applied to missing individual questions first, and the value of the total (or sub-scale) score will be derived based on the imputed individual questions.

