3. **Worst Observation Carried Forward (WOCF):** The worst observed post-baseline value will be used to replace missing values for continuous variables. For questionnaire-based variables, WOCF will be applied to missing individual questions first, and the value of the total (or sub-scale) score will be derived based on the imputed individual questions.
4. **Observed Case (OC):** No data will be imputed. The observed values are used in analysis, including assessments post rescue medication.
5. **Pattern-mixture model under assumption missing not at random (MNAR), controlled-based pattern imputation:** refer to the 3 phases for MI-based imputation above. With controlled-based pattern imputation, only observations in placebo treatment group are used to derive the imputation model.

Binary endpoints:

All missing values will be treated as a Non-Responder for the binary endpoints. If a subject withdraws from the study, all assessment after withdrawal will be considered as Non-Responder.

LOCF, OC, MI and Pattern-Mixture Model under missing not at random assumption approaches will be used as sensitivity analysis to impute the missing values for the selected secondary endpoints as appropriate. For sensitivity analyses, binary endpoints will be analysed using **Cochran-Mantel-Haenszel (CMH)** test stratified by baseline IGA severity.

There will be no imputations for missing laboratory and vital sign data.

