4.9.3 Quality of Life and Productivity data Analyses

Primary study population for all QoL and productivity data analyses will be based on ITT population. The DLQI, HADS, EQ5D and productivity data will be summarized by treatment group and visit.

By-subject listings of these data should be provided.

4.9.3.1 Change from baseline in DLQI at each visit up to week 24

This endpoint will be analyzed as the primary efficacy endpoint using a MMRM approach.

In addition, the following analyses will be performed:

- A shift table (by visit) will be generated using the categories as described in Section 3.2.6.1.
- Change from baseline in each sub-scale (see Section 3.2.6.1) at each visit up to week 24 will be analyzed as the primary efficacy endpoint using a MMRM approach.

- Proportion of subjects achieving a change in DLQI score of at least 4 points at each visit up to week 24 will be analyzed using a CMH test as described in Section 4.7.3.1.

4.9.3.2 Change from baseline in HADS at each visit up to week 24

The following endpoints will be analyzed as the primary efficacy endpoint using a MMRM approach.

- Change from baseline in HADS anxiety sub-score at each visit up to week 24
- Change from baseline in HADS depression sub-score at each visit up to week 24

In addition, the following analyses will be performed using a CMH test as described in Section 4.7.3.1:

- Proportion of subjects with HADS anxiety sub-score ≥ 11 at each visit up to week 24
- Proportion of subjects with HADS depression sub-score ≥ 11 at each visit up to week 24

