- If there is a response between two tick boxes, the lower of the two score options should be recorded.
- The DLQI can be analyzed by calculating the score for each of its six sub-scales (see above). When using sub-scales, if the answer to one question in a sub-scale is missing, that sub-scale should not be scored.

Minimal Clinically Important Difference of the DLQI

For **general inflammatory skin conditions** a change in DLQI score of at least 4 points is considered clinically important (Basra et al, 2015). This means that a subject's DLQI score has to either increase or decrease by at least 4 points in order to suggest that there has actually been a

meaningful change in that subject's quality of life since the previous measurement of his/her DLQI scores.

Reference

Basra MK et al. Determining the minimal clinically important difference and responsiveness of the Dermatology Life Quality Index (DLQI): further data. *Dermatology*, 2015; 230(1):27-33.

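### Two supportive quality-of-life proportions can mislead if run as written: the DLQI 4-point change has no direction, and on a literal reading missing HADS lands in the favourable category

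*SAP*

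**What the plan says.** **DLQI.** SAP 4.9.3.1 plans a stratified CMH test, each dose against placebo, of the "Proportion of subjects achieving a change in DLQI score of at least 4 points at each visit up to week 24". It gives no direction. Appendix 3, explaining the 4-point threshold, says that a subject's "DLQI score has to either increase or decrease by at least 4 points" to suggest a meaningful change. SAP 3.2.6.1 states that higher DLQI scores mean poorer quality of life.

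**HADS.** SAP 4.9.3.2 plans the same test for the "Proportion of subjects with HADS anxiety sub-score ≥ 11 at each visit up to week 24" and the "Proportion of subjects with HADS depression sub-score ≥ 11 at each visit up to week 24". SAP 3.2.6.2 labels this band "11-21 = Abnormal (case").

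**Missing data.** SAP 4.9.3 has no missing-data rule of its own. The only rule for binary endpoints is in SAP 4.7.1.3: "All missing values will be treated as a Non-Responder for the binary endpoints". It continues: "If a subject withdraws from the study, all assessment after withdrawal will be considered as Non-Responder". On rescue, the same section says: "All efficacy data, except Observed Case (OC), will be set to missing after rescue medication is used", and it regards rescued subjects as treatment failures.

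**Who is analysed.** SAP 4.9.3 uses the ITT population, which is all randomized subjects. SAP 3.2.6.1 and 3.2.6.2 restrict both questionnaires to subjects fluent in a language in which they are available.

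**The concern.** A responder analysis needs two things fixed in advance: which direction is favourable, and where a subject without data goes.

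The DLQI proportion lacks the first. Improvers and worseners fall in the same numerator, so if placebo subjects worsen more often, the placebo rate rises and the treatment difference shrinks. Elsewhere the SAP does state direction: its secondary endpoints (3.2.2.2) specify an improvement for pruritus NRS and a reduction for IGA.

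The HADS proportions lack the second. Non-responder imputation is conservative when the counted event is a success. Here the counted event is a bad outcome, so scoring missing as no event gives the subject the good outcome. Withdrawn subjects would count as free of anxiety or depression, as would rescued subjects if the rescue rule covers HADS. That runs against the treatment-failure intent of 4.7.1.3. ITT subjects never given the questionnaire would fall in the same cell.

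At stake are supportive p-values for each dose against placebo, and how they are read beside the main quality-of-life results.

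**Working it through.** The plan states no figure for these proportions, so there is none to reproduce. The point rests on wording; the arithmetic only shows what the wording can do. The 50 subjects per arm (SAP 4.10) and the two-sided 5% level (SAP 4.2) are from the documents. All rates below are assumptions.

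**DLQI.** Let *i* be the proportion improving by at least 4 points and *w* the proportion worsening by at least 4 points.

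- Decrease only: event rate = *i*
- Either direction: event rate = *i* + *w*

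Assume *i* = 50% on placebo and 70% on active. The decrease-only difference is 70 − 50 = 20 points. The power of a simple two-proportion comparison with 50 per arm is 0.53.

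| Worsening, placebo / active | Either-direction rates | Difference | Power |
|---|---|---|---|
| 5% / 2% | 55% / 72% | 17 points | 0.42 |
| 10% / 5% | 60% / 75% | 15 points | 0.36 |
| 15% / 5% | 65% / 75% | 10 points | 0.19 |

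The loss equals *w*(placebo) − *w*(active). It is zero if worsening is equally common, and becomes a gain if active worsens more.

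**HADS.** Let *p* be the true case rate, the same in both arms and in subjects with and without data, and *m* the proportion missing.

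- Missing = not a case: observed rate = *p*(1 − *m*)
- Missing = case: observed rate = *p*(1 − *m*) + *m*

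With *p* = 20% and *m* = 30% on placebo and 15% on active:

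- Missing = not a case: 0.20 × 0.70 = 14% and 0.20 × 0.85 = 17%, active minus placebo +3 points.
- Missing = case: 0.14 + 0.30 = 44% and 0.17 + 0.15 = 32%, active minus placebo −12 points.

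The true difference is zero in both. Over a range (placebo / active, then active minus placebo):

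| True caseness | Missing | Missing = not a case | Missing = case |
|---|---|---|---|
| 10% | 30% / 15% | 7.0% / 8.5% (+1.5) | 37.0% / 23.5% (−13.5) |
| 10% | 40% / 20% | 6.0% / 8.0% (+2.0) | 46.0% / 28.0% (−18.0) |
| 20% | 30% / 15% | 14.0% / 17.0% (+3.0) | 44.0% / 32.0% (−12.0) |
| 20% | 40% / 20% | 12.0% / 16.0% (+4.0) | 52.0% / 36.0% (−16.0) |
| 30% | 30% / 15% | 21.0% / 25.5% (+4.5) | 51.0% / 40.5% (−10.5) |
| 30% | 40% / 20% | 18.0% / 24.0% (+6.0) | 58.0% / 44.0% (−14.0) |
| 20% | 10% / 10% | 18.0% / 18.0% (0) | 28.0% / 28.0% (0) |
| 20% | 15% / 30% | 17.0% / 14.0% (−3.0) | 32.0% / 44.0% (+12.0) |

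The two readings give opposite signs whenever missingness is unequal. Turning the endpoint round, to below 11 with missing as not achieved, does not help. It gives 0.80 × 0.70 = 56% against 0.80 × 0.85 = 68%, the same spurious 12 points.

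**The case against.** A reader might infer that both endpoints are coded backwards. The documents do not support that. The DLQI proportion is undirected, not reversed, because improvements still count. Counting HADS sub-scores of 11 or more is an ordinary way to report an adverse state, and it matches the SAP's own category.

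A reader might also infer that the SAP says missing HADS means not a case. It does not. The non-responder sentence belongs to the efficacy section (4.7), whereas quality of life is under other analyses (4.9). Section 4.9.3 borrows only the CMH test from 4.7.3.1, which itself cites 4.7.1.3 only for sensitivity analyses. Non-responder is not defined for caseness, the treatment-failure language points the other way, and SAP 4.2 uses subjects with data as the denominator for descriptive percentages. All of that stands. It shows that the handling is unspecified, not that it is settled: 4.7.1.3 covers the binary endpoints without exception and no other rule exists. The schedule in SAP Appendix 1 also groups DLQI and HADS with the efficacy and subject-reported assessments.

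On DLQI, one can argue that the wording about achieving a change, together with the success language of 4.7.3.1, implies improvement, and that Appendix 3 explains an important difference in general without defining this endpoint. That may well be the intent. But the endpoint names no direction, and the only gloss on the threshold names both.

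Finally, every rate is assumed, and 3 points in 50 subjects is 1.5 subjects. Where placebo has more missing data and more worsening, both effects work against the drug. That stands and limits the severity.

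**Conclusion.** The point holds as a minor one. The DLQI part follows directly from the text: a worsening of 4 points meets the event as written. Under the assumed rates, a 20-point difference falls to between 10 and 17 points. The HADS part is an inference from the literal reading of the only available rule. With 10% to 30% true caseness and missingness of 30% against 15% or 40% against 20%, that reading creates a false difference of 1.5 to 6 points against the arm with more complete data. The opposite reading creates 10.5 to 18 points in that arm's favour. Neither creates a difference if missingness is equal.

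The primary endpoint, the sample size and the MMRM analyses of DLQI and HADS do not depend on either definition, and the by-visit DLQI shift table would show worsening separately.

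**What to change.** Amend SAP 4.9.3 before database lock:

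1. **DLQI.** Define the event as a decrease of at least 4 points from baseline. Missing as non-responder is then coherent. State how subjects with a baseline score below 4, who cannot meet the definition, are handled.
2. **HADS.** State that the two caseness proportions are exempt from the non-responder rule. Use multiple imputation, which SAP 4.7.1.3 and 4.7.3.8 already provide for other binary endpoints. Say whether post-rescue HADS values are set to missing. Show missing = case only as a sensitivity analysis, because with the inputs above it turns no true effect into 44% against 32%.
3. **Denominator.** Restrict the HADS proportions to ITT subjects who were given the questionnaire. Say whether the same applies to DLQI, which has the same language restriction.

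The cost is a few sentences and one imputation program for two supportive endpoints. No data collection changes.

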Quality-of-life (QoL) assessment:	
 - Dermatology Life Quality Index (DLQI) at baseline, weeks 2, 12 & 24 - Hospital Anxiety and Depression Scale (HADS) at baseline, weeks 12 & 24 - Missed work/school days to be recorded at weeks 4, 8, 12, 16, 20 & 24 - EuroQoL 5-Dimension (EQ5D) at baseline and week 24

Principal statistical method:
	
Primary inference for all the efficacy analyses will be based on the intent-to-treat (ITT) population at the week 24 endpoint. The primary endpoint will be analyzed using a Mixed-effect Model for Repeated Measures (MMRM) approach, including terms of treatment group, and baseline IGA severity. Visit will be fitted as a categorical variable, with the effect of treatment group and baseline varying at each visit.
 
Continuous secondary efficacy endpoints will be analyzed in a similar manner to the analysis of the primary endpoint. All categorical efficacy endpoints will be analyzed using a stratified Cochran Mantel-Haenszel test.
 
Multiple comparison procedures-modeling (MCP-Mod) approach will be applied using a set of candidate dose-response models to test for a dose-response relationship via model-associated statistics.
 
Exposure-response modeling will also be conducted for the primary endpoint of EASI percentage change from baseline at week 24, and for percentage change in pruritus NRS at week 4.
 
Primary inference for all the safety analyses will be based on the safety population. A summary of safety endpoints (treatment-emergent adverse events [TEAE], vital signs, laboratory parameters and ECG etc.) will be presented by treatment group.
 
To impute the missing values for continuous endpoints, mixed-effect MMRM approach will be used for the primary and secondary endpoints. All missing values will be treated as a non-responder for binary endpoints. All efficacy data, except in observed case analysis, will be set to missing after rescue medication is used.

Sample size:
	
Sample size is estimated using MCP-Mod approach by selecting a set of candidate dose response shapes based on primary endpoint response (percent change in EASI). Assuming placebo response of 35%, standard deviation 45% and a maximum treatment difference of 30%, 50 subjects per arm will provide at least 90% power to detect a statistically significant dose-response for at least one model at 1-sided significance level of 0.025.

Table 1 Clinical trial schematic

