4.7.3 Secondary Efficacy Endpoints

For analyses up to week 24 using the MMRM approach for continuous endpoints, only data collected up to week 24 will be included in the model.

4.7.3.1 Proportion of subjects achieving IGA success (defined as IGA 0 [clear] or 1 [almost clear]) at each visit up to week 24

A CMH test stratified by baseline IGA severity (3, 4) will be used to test the difference between each nemolizumab regimen and the placebo for the proportion of subjects achieving certain “success” at a given visit for ITT and PP populations. A 95% CI for the treatment difference will be calculated.

A bar chart and line plots will be produced over time for each treatment group to summarize the data (“responders”).

Sensitivity analysis: Sensitivity analyses will be performed as described in 4.7.1.3.

Subgroup analysis: Subgroup analyses will be investigated as described in 4.7.1.6.

Logistic regression will be used with response status as the dependent variable and treatment group, subgroup factor and interaction between treatment group and subgroup as independent variables. Odds ratios and the respective 95% CIs will be used for all subgroup comparisons. In addition, the p-values for the interaction of the treatment groups and the subgroups will also be provided, wherever appropriate.

4.7.3.2 Proportion of subjects achieving IGA success (defined as IGA 0 [clear] or 1 [almost clear]) and a reduction of at least 2 points at each visit up to week 24

This endpoint will be analyzed as described in section 4.7.3.1.

4.7.3.3 Percent change from baseline in EASI at each visit up to week 24

This endpoint will be analyzed as the primary efficacy endpoint using a MMRM approach for ITT and PP populations.

4.7.3.4 Absolute and percent change from baseline in weekly average of the peak and average pruritus NRS at each visit up to week 24

The following endpoints will be analyzed as the primary efficacy endpoint using a MMRM approach for ITT and PP populations.

- Absolute change from baseline in weekly average of the peak pruritus NRS at each visit up to week 24
- Percent change from baseline in weekly average of the peak pruritus NRS at each visit up to week 24
- Absolute change from baseline in weekly average of the average pruritus NRS at each visit up to week 24
- Percent change from baseline in weekly average of the average pruritus NRS at each visit up to week 24

The plots showing the changes over time within each treatment group will be provided.

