4.9.3.3 Missed work/school day in the past 4 weeks by visit

This endpoint will be analyzed using an analysis of variance (ANOVA), with treatment group and baseline IGA severity (3, 4) as covariates in the model. A 95% CI for the difference between each nemolizumab dose regimen and placebo in LSMeans and p-value will be calculated based on contrast test statistics.

Total number of missing days during the treatment period will be summarized by treatment group.

4.9.3.4 Change from baseline in EQ5D at week 24

The following endpoints will be analyzed using ANCOVA, with treatment group, baseline IGA severity (3, 4) and baseline values of the corresponding response variable as covariates in the model. A 95% CI for the difference between each nemolizumab dose regimen and placebo in LSMeans and p-value will be calculated based on contrast test statistics.

- Change from baseline in EQ5D index at week 24
- Change from baseline in EQ5D VAS at week 24
- Change from baseline in each dimension score of EQ5D at week 24

In addition, number and percentage of subjects in each level of each dimension of EQ5D will be summarized at week 24. The difference between each nemolizumab dose regimen and placebo will be tested using CMH tests based on ridit scores stratified by baseline IGA severity (3, 4).

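### The supplementary tests of HADS caseness and EQ5D levels ignore the baseline status already collected, which costs precision but not validity

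*SAP*

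**What the plan says.** SAP 4.9.3.2 is headed as change from baseline in HADS. Its lead analysis is an MMRM of each sub-score, run like the primary endpoint, and SAP 4.7.2 puts the corresponding baseline value in that model. It then adds tests of caseness: "Proportion of subjects with HADS anxiety sub-score ≥ 11 at each visit up to week 24", and the same for depression. For these, "the following analyses will be performed using a CMH test as described in Section 4.7.3.1", and that section reads: "A CMH test stratified by baseline IGA severity (3, 4) will be used to test the difference between each nemolizumab regimen and the placebo".

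SAP 4.9.3.4 follows the same pattern. Its lead analyses are ANCOVAs of the EQ5D index, the VAS and each dimension score, all with the baseline value as covariate. In addition, the "number and percentage of subjects in each level of each dimension of EQ5D will be summarized at week 24", and the difference from placebo "will be tested using CMH tests based on ridit scores stratified by baseline IGA severity (3, 4").

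The baseline values exist. SAP 3.2.6.2 states: "HADS will be assessed at baseline, weeks 12, 24, or early termination visit when applicable". The Protocol synopsis lists "EuroQoL 5-Dimension (EQ5D) at baseline and week 24". Neither scale is an eligibility criterion or a randomization stratum; IGA is the only stratification factor (Protocol 6.1.4).

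**The concern.** Caseness at week 24 and EQ5D level at week 24 are states, not changes. A subject who was a case throughout counts the same as one who became a case during treatment. The strongest likely predictor of the state at week 24 is the state at baseline, and the planned tests leave it out. They stratify by a skin score that may say little about anxiety, depression or general health.

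Two things follow. First, the tests have less power than the collected data allow. Second, arms of 50 or fewer can differ at baseline by chance, and part of that difference appears at week 24. A caseness p-value could then disagree with the baseline-adjusted MMRM of the same sub-scale only because one arm started with more cases.

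The affected tests are 2 HADS sub-scales × 2 visits × 3 doses = 12 comparisons, and 5 EQ5D dimensions × 3 doses = 15 comparisons.

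**Working it through.** **The plan's own figure.** The plan states no power for HADS or EQ5D. Its only power statement (SAP 4.10) is at least 90% for the EASI dose-response test. Simulating that test gives 92.9% to 98.3% over the nine candidate shapes if the 30-point difference is reached at 90 mg. It does not bear on this point.

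**Inputs from the documents.** 50 per arm, 1:1:1:1 allocation, two-sided 5% (SAP 4.2), CMH stratified by IGA 3 or 4.

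**Inputs assumed, because the documents give none.** Baseline caseness 20% to 40%; 40% of subjects at IGA 4; latent baseline to week 24 correlation 0.4, 0.6 or 0.8. Each comparison is one dose against placebo, with 20,000 simulated comparisons for HADS and 15,000 for EQ5D. The test stratified by IGA is set against the test stratified by IGA and baseline status.

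**Step 1: size of chance imbalance.** SD of the between-arm difference in baseline caseness = sqrt(2 × p × (1 − p) / n). At p = 0.30 and n = 50 this is sqrt(2 × 0.3 × 0.7 / 50) = 0.092, about 9 points. A difference of at least 15 points is 0.15 / 0.092 = 1.6 SD, so it arises in about 10% of comparisons. A difference of at least 10 points arises in 26% to 35% over caseness of 20% to 40%.

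**Step 2: HADS with no true effect, 30% baseline caseness.**

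| Correlation | Overall rejection, IGA only | Share of each imbalance point carried to week 24 | Rejection given imbalance ≥15 points, IGA only | Same, with baseline stratum |
|---|---|---|---|---|
| 0.4 | 4.9% | 0.24 | 7.4% | 5.9% |
| 0.6 | 5.0% | 0.39 | 10.4% | 5.7% |
| 0.8 | 5.2% | 0.57 | 18.5% | 5.3% |

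At correlation 0.6, a 15-point imbalance moves the week 24 difference by 0.39 × 15 = about 6 points. About 2,000 comparisons (10% of 20,000) lie behind each conditional rate, so the standard error is about 0.6 to 0.9 points on the IGA-only rates.

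**Step 3: HADS power.**

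| Baseline cases | Week 24 cases, placebo v active | IGA only | With baseline stratum, correlation 0.4 / 0.6 / 0.8 |
|---|---|---|---|
| 30% | 30% v 10% | 74% | 74% / 78% / 84% |
| 30% | 25% v 8% | 65-66% | 66% / 69% / 76% |
| 40% | 35% v 15% | 65-66% | 67% / 71% / 78% |
| 20% | 20% v 5% | 66% | 65% / 69% / 75% |
| 40% | 40% v 20% | 60-61% | 62% / 66% / 75% |

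From the unrounded results, the gain is about 0-2 points at 0.4, 3-6 at 0.6 and 9-14 at 0.8.

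Very strong persistence gives more. Take 30% cases at baseline, of whom 80% on placebo and 40% on active remain cases, with 10% and 4% new cases. Power rises from 50% to 67% without the IGA strata, and from 49% to 65% with them. This scenario corresponds to a latent correlation of about 0.89 on placebo.

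**Step 4: EQ5D.** Baseline levels are assumed at 30%, 55% and 15%, and placebo week 24 levels at 40%, 50% and 10%. For a latent shift of 0.5 SD, the IGA-only ridit test has 56% power. With all three baseline levels as strata it has 58%, 64% and 76% at correlations 0.4, 0.6 and 0.8. Repeating the simulation with baseline collapsed to no problems versus any problems gives 58%, 62% and 68%. With no true effect and a mean-level imbalance of at least 0.2 (11.5% of comparisons), the IGA-only test rejects in 8% to 20%, against about 6% with three-level baseline strata.

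**The case against.** The strongest reply is that randomization already makes these tests valid. That stands: overall rejection with no true effect is 4.8% to 5.2% for HADS and 5.0% to 5.2% for EQ5D. A reader might infer that the tests are biased, or that a baseline difference is read in full as a treatment effect. The documents do not support that. The effect is conditional on the imbalance that happens to occur, and only about 0.2 to 0.6 of each point carries over.

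These tests are also additions. Baseline-adjusted analyses lead in both sections, and for EQ5D they include each dimension score, so the same three-level items already get an adjusted test. HADS and EQ5D are not among the primary, secondary or other efficacy endpoints in SAP 3.2.2, and the sample size rests on EASI alone. All this stands and keeps the priority low. It does not adjust the caseness and level tests themselves. The allowance in SAP 4.7.2 for exploring other covariates concerns the MMRM. The named shift table in 4.9.3.1 is for DLQI only.

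A third reply is that a gain of 11 to 17 points would be the favorable end. That is right: such figures need latent placebo correlations of about 0.86 to 0.90, and at 0.4 the HADS gain is close to zero.

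Finally, IGA crossed with three EQ5D levels makes six strata for about 100 subjects, or fewer, because the questionnaires go only to those fluent in an available language. Extreme levels may be empty or present in one arm only. This also stands, and the fix allows for it.

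**Conclusion.** The point holds as a cheap improvement to supplementary quality-of-life tests. HADS caseness and week 24 EQ5D levels are compared without the baseline status that the trial collects and that the companion models use. The cost is lost precision and some exposure to chance imbalance, not an inflated overall error rate.

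At 30% baseline caseness and an imbalance of at least 15 points, false rejection for HADS is roughly 7% to 18%, against 5% to 6% with a baseline stratum. The HADS power gain runs from nothing to about 14 points over correlations 0.4 to 0.8, with about 17 as the extreme. All of this depends on assumed caseness rates and correlations.

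A reader might extend the point to IGA success, because SAP 4.7.3.1 supplies the method. That would be wrong: there the stratum, baseline IGA, is the baseline of the same variable. The DLQI responder test in 4.9.3.1 is defined on change and is not affected in the same way.

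**What to change.** - **SAP 4.9.3.2:** stratify the HADS CMH tests by baseline caseness of the same sub-scale (≥11 or <11) as well as baseline IGA.
- **SAP 4.9.3.4:** stratify the ridit CMH test by baseline level of the same dimension, collapsed to no problems versus any problems, as well as baseline IGA.
- **Both:** put subjects with no baseline score in a separate stratum, so that none is dropped.

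The cost is a few lines of SAP text and one more stratification variable in existing code, with no new data or visits. The small downside is that some strata may be sparse and add little information. Collapsing the EQ5D levels limits this but gives up part of the gain at high correlation (68% rather than 76% power at 0.8 in the example). The change should be written in before unblinding, because an adjustment chosen after an imbalance is seen would be post hoc.
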